## 1 Introduction:

Canadian Cancer Trials Group (CCTG) MA.38 is a randomized phase II trial to estimate the hazards ratio of the progression-free survival of two different dose regimens of palbociclib in combination with endocrine therapy (fulvestrant or tamoxifen or Aromatase Inhibitor) as second line therapy in women with ER positive, HER2 negative, advanced/metastatic breast cancer. This document is to describe the statistical analysis plan for the final analysis of MA.38.

### 1.1 Objectives

The **primary objective** of this trial is to **estimate** the hazard ratio of the progression-free survival (PFS) of two different dose regimens of palbociclib in combination with endocrine therapy (fulvestrant or tamoxifen or Aromatase Inhibitor). The **Secondary Objectives** include evaluating the following endpoints: Safety and Tolerability, Response Rate Duration of Response, Clinical Benefit Rate, Overall Survival (OS) and Quality of Life (QoL).

### 1.2 Sample Size Determination

The objective of this trial was neither to test superiority nor to test noninferiority between two arms. The sample size is based on estimating the hazard ratio (HR) of two arms (experimental vs. control) within a 90% confidence interval (CI). For a 1:1 randomization with 1 year accrual and one-year additional follow-up. If we observe approximately 58 progression events in each arm, the upper bound of the 90% CI will be 1.36 times the estimated HR and the lower bound will be 0.74 times the estimated HR. Assuming a median PFS of approximately 10 months for both treatment arms, duration of accrual and follow-up both at 1 year, and a dropout rate of 10%, the study would need to enroll approximately 90 subjects in each arm.

### 1.3 Timing of the Analyses

There will be no interim analysis for efficacy. An interim safety analysis was conducted in August, 2016, when 24 patients were enrolled and evaluable for toxicity. The final analysis will be conducted with a total of 116 PFS events observed. This is expected to happen two years after the trial activation.

### 1.4 Data Collection

Data are collected, entered and managed by CCTG, Kingston, Ontario, according to the group standard data management procedures. The clinical cut-off date will be April 16, 2018.

## 2 Methods and Analyses

### 2.1 Analyses Samples

Patients were randomized to the following two treatment arms:

- Arm 1: Palbociclib 100 mg po daily.
- Arm 2: Palbociclib 125 mg po daily 3 out of 4 weeks

The study populations for this analysis will include both the intention to treat (ITT) population and the as treated population.

Analysis of pretreatment characteristics and all efficacy outcomes such as PFS and OS, will be based on the ITT population. The efficacy data set consists of all patients regardless of actual treatment.

Those who received at least one dose of protocol therapy (i.e. the as treated population) will form the basis of the safety analyses. The response analyses will include patients with measurable disease or those with non measurable disease who experience a CR. QOL analyses will include all patients who completed at least one QOL assessment (either baseline or follow-up).

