#### 2.5.1.3 Response Rate

Response will be evaluated in this study using the revised international RECIST Criteria (1.1)

All patients who have received at least one dose of therapy and have their disease re-evaluated will be considered evaluable for response (exceptions will be those who exhibit objective disease progression prior to the end of cycle 1 who will also be considered evaluable). Patients on therapy for at least this period and who meet the other listed criteria will have their response classified as CR, PR, SD and PD. Patients with non measurable disease will only have a best response of either CR or 'Non CR/Non PD'.

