#### 2.5.1.5: Clinical Benefit Rate

Clinical benefit includes patients with documented CR, RP or SD for those with measurable disease and CR for with non measurable disease.

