#### 2.5.2.3 Response Rate and Clinical Benefit Rate

Response rates (percentages of CR/PR as best response) will be reported by treated arms for patients evaluable for response.

Clinical benefit rates (percentages of CR/PR/SD as best response) will be reported by treated arms for patients evaluable for response.

Response rates and clinical benefit rates will be compared between two arms using the Cochran-Mantel-Haenszel test adjusting for stratification factors at randomization (Table 16).

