Other condition or circumstance			
Patients who were censored			
Reason Censored			
Still Alive			
Withdrawal of Consent			

*Table 16: Response to Treatment*

	Number of Patients (%)		
	Data set: All treated patients with measurable disease		
	Palbociclib 100mg N = ***	Palbociclib 125mg N = ***	
Response to treatment			
CR	XX (%)	XX (%)	XX (%)
PR			
SD			
PD			

\*Stratification CMH test p-value for response rate:  $(CR+PR)/(CR+PR+SD+PD)$

\*\*Stratification CMH test p-value for clinical benefit rate:  $(CR+PR+SD)/(CR+PR+SD+PD)$

*Table 17: Duration of Response*

	Number of Patients (%)		
	Data set: All patients with CR/PR		
	Palbociclib 100mg N = ***	Palbociclib 125mg N = ***	Stratified p-value from log rank test
Duration of response			
Median	XX	XX	p-value =
Min	XX	XX	-
Max	XX	XX	-
Q1	XX	XX	-
Q3	XX	XX	-

*Table 18: Dose information*

Data set: All treated Patients: Cumulative dose (mg)			
	Number of patients		
	Palbociclib 100mg N = ***	Palbociclib 125mg N = ***	Total N = ***
Median	***	***	***
Min	**	**	**
Max	**	**	**
Q1			
Q3			

Cumulative dose (mg)

n

Mean

Std

Median

Min

Max

Q1

Q3

*Similar tables for*

*Daily dose(mg),*

*Dose intensity (mg/week)*

*Relative dose intensity (percent)*

*Cycle 1 and 2 dose intensity (mg/week)*

*Cycle 1 and 2 relative dose intensity (percent)*

90% or more dose intensity: N and percent

Data set: All treated Patients			
90% or more dose intensity: N and percent	Number of patients		
	Palbociclib 100mg N = ***	Palbociclib 125mg N = ***	Total N = ***
No	***	***	***
Yes	**	**	**

Cycle 1 and 2 90% or more dose intensity: N and percent

Data set: All treated Patients			
Cycle 1 and 2 90% or more dose intensity: N and percent	Number of patients		
	Palbociclib 100mg N = ***	Palbociclib 125mg N = ***	Total N = ***
No	***	***	***
Yes	**	**	**

*Table 19: Dose modifications*

Data set: All treated Patients			
At least one dose modification	Number of patients		
	Palbociclib 100mg N = ***	Palbociclib 125mg N = ***	Total N = ***
Yes	**	**	**
Reason of dose modifications Reason 1 Reason 2 ...			

Data set: All treated Patients			
At least done dose Reduction	Number of patients		
	Palbociclib 100mg N = ***	Palbociclib 125mg N = ***	Total N = ***
Yes	**	**	**
Reason of dose reduction Reason 1 Reason 2 ...			

Data set: All treated Patients			
Patients with dose discontinuation	Number of patients		
	Palbociclib 100mg N = ***	Palbociclib 125mg N = ***	Total N = ***
Yes	**	**	**
Reason of dose discontinuation			

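### The response set in SAP section 2.1 selects non-measurable patients on their outcome, and sections 2.5.1.3 and 2.5.2.3 and Table 16 treat the same patients differently

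*SAP*

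**What the plan says.** The SAP describes the patients behind the response rate and the clinical benefit rate in five places.

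- **Section 2.1:** "The response analyses will include patients with measurable disease or those with non measurable disease who experience a CR". The same section places efficacy outcomes in general on the ITT population.
- **Section 2.5.1.3:** "All patients who have received at least one dose of therapy and have their disease re-evaluated will be considered evaluable for response". Patients with objective progression before the end of cycle 1 are evaluable too. Measurability is not a condition, and non-measurable patients are given their own categories: "Patients with non measurable disease will only have a best response of either CR or 'Non CR/Non PD".
- **Section 2.5.1.5:** "Clinical benefit includes patients with documented CR, RP or SD for those with measurable disease and CR for with non measurable disease".
- **Section 2.5.2.3:** "Response rates (percentages of CR/PR as best response) will be reported by treated arms for patients evaluable for response". The clinical benefit rate has the same denominator. Both rates are compared between arms by a stratified Cochran-Mantel-Haenszel (CMH) test, and the reader is sent to Table 16.
- **Table 16:** the data set is "All treated patients with measurable disease". The rows are CR, PR, SD and PD, and the footnotes use the sum of these four as the denominator of both rates.

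Table 17, on duration of response, takes "All patients with CR/PR".

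**The concern.** There are two faults.

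The first is selection on the outcome. Under section 2.1, each CR in a non-measurable patient adds one to the numerator and one to the denominator. A non-measurable patient without CR adds to neither. Membership of the set thus depends on the result being estimated.

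The second is that three different sets are in force. Non-measurable CRs are in under sections 2.1 and 2.5.1.3 but out under Table 16. Non-CR/Non-PD patients are in only under section 2.5.1.3. No order of precedence is given. Section 2.5.1.5 counts non-measurable CRs as clinical benefit, yet the table that reports that rate excludes those patients.

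Both rates are secondary objectives, and section 2.3 tests comparisons at two-sided 5% unless otherwise specified. The SAP is dated 2018-08-08 and the clinical cut-off is April 16, 2018, so the choice of denominator is still open after cut-off. A SAP should close such a choice, whether or not anyone would misuse it.

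**Working it through.** The SAP states no response rate, clinical benefit rate or share of non-measurable disease, so there is no figure of its own to reproduce. The check computes each rate under each rule.

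**Notation, per arm.** M is the number with measurable disease, R their CR/PR count and B their CR/PR/SD count. U is the number with non-measurable disease and C the CRs among them.

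**Response rate under each rule** (for clinical benefit, replace R by B):

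- Table 16: R/M
- Section 2.1: (R + C)/(M + C)
- Sections 2.5.1.3 and 2.5.2.3: (R + C)/(M + U)

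**Example.** The 90 patients per arm come from section 1.2. The rest is assumed: M = 60, R = 15, B = 45, U = 30, C = 2, all treated and re-evaluated.

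| Rule | Response rate | Clinical benefit rate |
|---|---|---|
| Table 16 | 15/60 = 25.0% | 45/60 = 75.0% |
| Section 2.1 | 17/62 = 27.4% | 47/62 = 75.8% |
| Sections 2.5.1.3 and 2.5.2.3 | 17/90 = 18.9% | 47/90 = 52.2% |

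**Dependence on C.** With C = 0 the three response rates are 25.0%, 25.0% and 15/90 = 16.7%. With C = 3 they are 25.0%, 18/63 = 28.6% and 18/90 = 20.0%.

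**Table 16 footnote applied to the section 2.5.1.3 set.** The 28 Non-CR/Non-PD patients have no cell and drop out, while the 2 CRs stay. The result is 17/62 = 27.4%, so the selection of section 2.1 returns. Any non-measurable patient recorded as PD would also stay, but section 2.5.1.3 does not list that category for them.

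**Responder counts.** In the example Table 17 would hold 17 responders, against 15 with CR or PR in Table 16.

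**Range.** All values are assumed: N = 90, non-measurable share s of 20 to 40%, measurable response rate of 15 to 30%, measurable clinical benefit rate of 60 to 80%, and non-measurable CR rate q of 0 to 10%. Let p be the measurable rate (response or clinical benefit).

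*Section 2.1 minus measurable-only* equals (1 − p) × C/(M + C).

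- The minimum is 0, when C = 0.
- The maximum is at s = 40% and q = 10%, so M = 54 and C = 3.6.
- Response rate with p = 15%: (8.1 + 3.6)/57.6 − 15% = 20.3% − 15% = 5.3 points.
- Clinical benefit with p = 60%: (32.4 + 3.6)/57.6 − 60% = 62.5% − 60% = 2.5 points.

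*Measurable-only minus all-evaluable* equals s × (p − q).

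- Response rate: from 0.2 × (0.15 − 0.10) = 1 point to 0.4 × (0.30 − 0) = 12 points.
- Clinical benefit: from 0.2 × (0.60 − 0.10) = 10 points to 0.4 × (0.80 − 0) = 32 points.

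**The case against.** The strongest reply is that the sections can be read together. Section 2.5.1.3 may only add two conditions, treated and re-evaluated, within the set of section 2.1. Sections 2.1, 2.5.1.3 and 2.5.1.5 and the Table 16 footnotes would then agree, and only the Table 16 heading would be out of line. On that reading the 1 to 12 and 10 to 32 point differences do not arise, because Non-CR/Non-PD patients are never in the denominator. The Table 17 mismatch would simply follow from the Table 16 heading.

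Part of this stands. The large differences rest on the literal wording of sections 2.5.1.3 and 2.5.2.3, and Table 17 is a consequence rather than a separate error. But the SAP does not state the joint reading. That reading also keeps the outcome-based selection of section 2.1 and still leaves the Table 16 heading in conflict.

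It is also fair to say that every size here is assumed, and that 5.3 points is one corner of the grid: 40% non-measurable, 10% CR and the lowest response rate. The worked example gives 2.4 points for response and 0.8 for clinical benefit. The rule is the same in both arms, so the contrast moves only if the number of non-measurable CRs differs by arm. Section 1.2 says the trial tests neither superiority nor noninferiority. These points limit the consequence but do not remove the fault.

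**Conclusion.** The concern holds. If section 2.1 is followed and at least one non-measurable CR occurs, both rates are biased upward against a measurable-only set. Under the assumed ranges the bias is 0 to 5.3 points for response and 0 to 2.5 points for clinical benefit. If Table 16 is followed, this bias does not occur.

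The open choice between a measurable-only and an all-evaluable denominator can move the rates more: 1 to 12 points for response and 10 to 32 for clinical benefit, on the literal reading of section 2.5.2.3. That shift is dilution, not bias, but the plan should not leave it undecided.

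The contradiction in the text is certain; its size depends on rates that the SAP does not give. It affects two secondary endpoints and should be fixed. The primary PFS analysis is untouched.

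**What to change.** - Define the response set in section 2.1 by baseline status only, for example patients with measurable disease at baseline, and use that set for both rates.
- Show non-measurable patients in a separate panel of Table 16, outside the rates, with a cell for Non-CR/Non-PD and, if it can be recorded, for PD.
- Align sections 2.5.1.3, 2.5.1.5 and 2.5.2.3 and the Table 16 heading and footnotes with that set. This takes non-measurable CRs out of the clinical benefit rate, so section 2.5.1.5 should first be checked against the protocol's definition. If those CRs must count, all evaluable non-measurable patients belong in the denominator as well.
- State whether non-measurable CRs enter Table 17, so that its responder count can be reconciled with Table 16.

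A separate, optional addition is a not-evaluable row in Table 16, with a sensitivity analysis that counts those patients as non-responders.

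The cost is wording in four sections, changes to two tables and one extra panel. No new data are needed. If any non-measurable CR occurs, the reported rates will be slightly lower than under section 2.1.

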## 2.2 Conventions for Calculating Key Data

In general, baseline evaluations are those collected closest, but prior to or on the day of randomization. If pre-randomization assessment was not done, a pre-treatment assessment will be used as baseline assessment.

When either day or month of a date is missing, the missing day and/or month will be imputed by the midpoints within the smallest known interval. For example, if the day of the month is missing for any date used in a calculation, the 15th of the month will be used to replace the missing day. If the month and day of the year are missing for any date used in a calculation, the first of July of the year will be used to replace the missing data.

## 2.3 Analysis Conventions

All comparisons between treatment arms will be carried out using a two-sided test at an alpha level of 5% unless otherwise specified. No formal adjustments will be made for the multiplicity of inferences for the other clinical endpoints.

Baseline stratification factors (excluding centre) that will be used to adjust the analyses where appropriate are listed below:

- Visceral metastases (yes versus no)
- duration of exposure to most recent endocrine therapy prior to randomization (4 groups)
  - duration  $\geq$  6 months versus  $<$  6 months in the advanced/metastatic setting
  - duration  $\geq$  24 months versus  $<$  24 months in the adjuvant setting
- Planned use of Fulvestrant versus Tamoxifen versus Aromatase Inhibitor (AI)

\*Add missing/unknown category whenever appropriate.

## 2.4 Randomization and Pre-treatment Characteristics

### 2.4.1 Definitions and Variables

#### 2.4.1.1 Accrual

- Number (%) of randomized patients per study center (table 1).

#### 2.4.1.2 Randomization/Stratification

A minimization procedure for treatment assignment was used in this study.

- Centre
- Visceral metastases (yes versus no)
- duration of exposure to most recent endocrine therapy prior to randomization (4 groups)
  - duration  $\geq$  6 months versus  $<$  6 months in the advanced/metastatic setting
  - duration  $\geq$  24 months versus  $<$  24 months in the adjuvant setting
- Planned use of Fulvestrant versus Tamoxifen versus Aromatase Inhibitor (AI)

Stratification factor at randomization (excluding centre) will be summarized by treatment arm (table 2).

Number and percentage of actual treatment received will be summarized by treatment arm (table 3).

#### 2.4.1.4 Ineligibility and Major Protocol Violations

Number and percentage of ineligible patients will be presented by treatment arm.

Reasons for ineligibility: percentage for each reason and combination of reasons of ineligibility will be presented by treatment arm.

The number and percentage of major protocol violations will be presented by treatment arm. (table 4)

#### 2.4.1.4 Summary of Follow-up

A table showing the median (calculated by KM method with inverse OS), min and max follow-up (defined as reverse censoring on survival) will be presented by treatment group and for all patients included in analysis. (table 5)

#### 2.4.1.5 Patient Characteristics

Patient characteristics at baseline are summarized in table 6.

- Age (Median, Q1 Q3, range)
- Age (40-49, 50-59, 60-69, 70+)
- Race
- ECOG PS
- Menopausal Status
- Visceral metastasis (at baseline)
- Duration of exposure to most recent endocrine therapy prior to randomization (at baseline)
- Planned use of endocrine therapy: Fulvestrant versus Tamoxifen versus Aromatase Inhibitor (at baseline)

- Histology
- ER status
- PR status
- Grade

\*An unknown category will be added when appropriate.

#### 2.4.1.6 Baseline Hematology/Biochemistry

CTC 4.0 grades will be used to summarize the baseline hematology/biochemistry data (% with each CTC grades) for the following assessments (table 7)

#### 2.4.1.7 Baseline Non-Hematologic Adverse Events

CTC 4.0 grades will be used to summarize the baseline Non-Hematologic (number for each CTC grades, total number and %) (table 8).

#### 2.4.1.8 Baseline Concomitant Medication

Number and percent of patients received concomitant medication will be summarized by treatment arm (table 9).

#### 2.4.2 Analysis of pre-treatment Characteristics

No formal statistical tests will be performed to assess the homogeneity of baseline characteristics between the arms. Categorical variables will be tabulated by treatment arm and for all patients. Continuous variables (e.g., age) will be presented using summary statistics (n, median, Q1, Q3, min and max) or specified cutoff categories by treatment arm and for all patients. Analyses will be based on all randomized patients by arm based on the ITT population.

### 2.5 Efficacy

#### 2.5.1 Definitions and Variables

##### 2.5.1.1 Progression-free Survival (PFS)

The primary endpoint is progression free survival (PFS) defined as time from randomization to progression or death from any cause. Disease progression will be investigator assessed using the RECIST 1.1 criteria. If a patient has not progressed or died at the time of final analysis, PFS will be censored on the date of the last disease assessment. If a patient received anti-cancer RT treatment, PFS will be censored at the date of anti-cancer treatment.

PFS Time (months) =

((date of PFS event or last disease assessment date - date of randomization) + 1) / 30.4375

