#### 2.5.2.1 Progression-free Survival

No formal statistical tests will be performed for PFS. A Kaplan-Meier curve for PFS in each treatment arm will be displayed.

The difference between the two treatment arms will be estimated using the **hazard ratio** stratified by the stratification factors at randomization (exclude centre).

The analysis of PFS will also be presented for each level of each stratification factor and hazard ratio with corresponding 90% CI will be reported. An un-stratified Cox regression model with stratification factors as

covariates will be fitted. In all regression analyses, all patients with missing value in any covariate will be deleted from the analysis. (Table 10, 11, Figure 1)

For patients who developed PFS events, the type of progression events and summary of progression will be tabulated (Table 12).

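### The RT-censoring sentence for PFS does not fit the PFS time formula and is not limited to RT before progression, and no PFS analysis without this potentially informative censoring is planned

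*SAP*

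**What the plan says.** SAP section 2.5.1.1 sets out the primary endpoint in four steps.

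- Definition: PFS is "defined as time from randomization to progression or death from any cause".
- General censoring rule, for patients without progression or death at the final analysis: "PFS will be censored on the date of the last disease assessment".
- RT rule: "If a patient received anti-cancer RT treatment, PFS will be censored at the date of anti-cancer treatment".
- Formula for PFS time in months: "date of PFS event or last disease assessment date - date of randomization) + 1) / 30.4375".

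Section 2.1 bases PFS on the ITT population: "The efficacy data set consists of all patients regardless of actual treatment". Section 2.5.2.1 plans a Kaplan-Meier curve, a stratified hazard ratio, hazard ratios by level of each stratification factor ("hazard ratio with corresponding 90% CI will be reported") and an unstratified Cox model with the factors as covariates. None of these changes or omits the RT rule. The Table 12 shell gives two reasons for censoring: no PFS event, and withdrawal of consent.

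**The concern.** The PFS hazard ratio is the result the trial exists to estimate, so each patient's PFS time and status should follow from the text in only one way. Three things in section 2.5.1.1 prevent that.

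1. The RT rule uses a date that the formula does not contain.
2. The rule has no time limit. It applies to any patient who received RT, including one whose progression was already recorded.
3. The trigger is first RT and then, later in the same sentence, anti-cancer treatment in general. RT is the likely meaning, but another programmer could include systemic therapy.

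There is also a question of checking. If RT is given because disease is about to progress, patients censored at RT are not a random sample of those still at risk. With no PFS analysis that follows patients past RT, and no separate count of RT-censored patients, a reader of the results could not tell whether the rule had influenced the hazard ratio.

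**Working it through.** **1. The plan's own figures.** Section 1.2 gives 58 events per arm and a 90% CI. The multiplier is exp(±1.645 × √(1/58 + 1/58)) = 1.357 and 0.737, which matches the stated 1.36 and 0.74. With exponential PFS, a median of 10 months, 12 months of accrual and 12 of follow-up, the probability of an event is 0.704. Then 116/0.704 = 164.7, and 164.7/0.9 = 183 patients, against about 180 stated. Both figures are reproduced. The sample size makes no separate allowance for RT censoring.

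**2. What the text does to individual patients.** The time is (days from randomization + 1)/30.4375.

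| Patient | RT sentence | Formula, without the RT sentence |
|---|---|---|
| No event, RT day 120, last assessment day 290 | censored, 121/30.4375 = 3.98 | censored, 291/30.4375 = 9.56 |
| Progression day 300, RT day 320 | censored, 321/30.4375 = 10.55 (literal reading) | event, 301/30.4375 = 9.89 |
| RT day 120, progression day 300 | censored, 3.98 | event, 9.89 |

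The first row shows two censoring dates for one patient. The second shows an observed event lost if the sentence is applied as written. In the third row the RT sentence gives a clear answer; the row shows only what is set aside by the rule.

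**3. RT date or last assessment before RT.** In simulation with 8-weekly assessments, the two choices gave average hazard ratios of 0.952 and 0.955 (RT in 10% vs 5% of patients) and 0.903 and 0.908 (15% vs 5%). They never differed by 5% in a single simulated trial. The choice does not matter numerically.

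**4. Possible bias.** The SAP gives no RT rates, so these are assumed. Trial-sized simulation: 180 patients, exponential PFS with a median of 10 months in both arms (true HR 1.00), 12 + 12 months, 10% dropout, unstratified Cox model, 4000 runs.

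| RT use, arm 1 / arm 2 | RT timing | Mean HR with RT censoring |
|---|---|---|
| 5% / 5% | 0-2 months before progression | 1.00 |
| 10% / 10% | 0-2 months before progression | 1.00 |
| 10% / 5% | 0-2 months before progression | 0.95 |
| 5% / 10% | 0-2 months before progression | 1.05 |
| 15% / 5% | 0-2 months before progression | 0.90 |
| 5% / 15% | 0-2 months before progression | 1.11 |
| 10% / 5% | 0-6 months before progression | 0.96 |
| 15% / 5% | 0-6 months before progression | 0.91 |
| 15% / 5% | unrelated to progression | 1.00 |

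A separate large-sample calculation, with RT about 1 month before progression, agrees: 0.997 (10% / 10%), 0.947 (10% / 5%), 0.898 (15% / 5%) and 1.109 (5% / 15%).

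**The case against.** The case on the other side is strong on several points.

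- A reader might infer that the RT rule contradicts the PFS definition or the ITT principle. It does not. A definition names the events and a censoring rule says when follow-up for them stops. ITT fixes which patients are analysed and in which arm. All randomized patients remain in the analysis.
- Censoring an already observed progression is an implausible reading, because time to first event has by then ended. That is probably the intention, but the restriction is not written down.
- Table 12 does not contradict the rule. A patient censored at RT has no counted PFS event and can sit under that row. The table merely fails to show how many such patients there are.
- A reader might infer that the primary hazard ratio will be biased. The SAP does not support this. It gives no RT rate and no reason for RT use to differ between two regimens of the same drug. Shifts of 0.90 to 1.11 need unequal use and RT close to progression at the same time.
- With equal use of 5% or 10%, hazard ratios with and without RT censoring differ by more than 5% in 21% or 39% of simulated trials. This is random variation from losing about 6 or 13 events, not bias.
- This is an estimation trial with no formal PFS test, and the SAP promises no robustness analysis that it then omits. The protocol, which is not shown, may clarify the RT rule.

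The formula mismatch, the missing time limit and the unclear trigger all stand, because they lie within one section of the SAP. The request for a supportive analysis also stands, as a low-cost check on the one primary estimate.

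**Conclusion.** The point holds as a defect of specification with an untested assumption attached. The RT sentence and the formula cannot both be applied as written, the sentence needs a limit to RT before any PFS event, and the treatments that trigger it need naming. RT censoring itself is a legitimate choice.

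The date ambiguity has a negligible effect on the hazard ratio. The effect of the censoring is about zero on average if RT use is equal or unrelated to progression, and roughly 5 to 10% if use differs by 5 to 10 percentage points shortly before progression. These sizes rest on assumed RT rates, exponential PFS, a fixed 24-month calendar and an unstratified model, whereas the SAP plans 116 events and a stratified hazard ratio. All of them lie well inside the multipliers of 0.74 to 1.36. The change should be made, but the point does not put the trial's conclusion in doubt.

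**What to change.** (a) In section 2.5.1.1, state that a progression or death before RT is always an event; that only RT starting before any PFS event triggers censoring, with later progression or death not counted in this analysis; and that RT alone counts, or which other treatments do. Keep the RT date and let the formula use the date of PFS event or censoring date. Moving to the last assessment before RT is optional and numerically immaterial.

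(b) In section 2.5.2.1, add a supportive PFS hazard ratio with 90% CI that counts the first RECIST progression or death regardless of RT. In Table 12, add a row for RT-censored patients by arm.

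The cost is a few lines of SAP text, one extra hazard ratio and one table row. Assessments after RT may be incomplete or affected by the RT itself, so the extra hazard ratio is supportive only.
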